6.2. NON INCLUSION CRITERIA

- Subject participating in another study including an exclusion period and still under way at inclusion.
- Administrative problems:

- inability to give parents or legal representatives expert information,
- no coverage by a Social Security regime
- Refusal by the parents or legal representative to sign the consent form.

NB: If a patient presents a contraindication for MRI, he/she can be included in the study but the MRI will not be carried out.

6.3. RECRUITMENT METHODS

For the group of children treated with OT:

The team from the reference centre will contact the families. There should not be any patients lost to follow-up, given that the patients who participated in the OTBB2 study and treated with OT are regularly monitored as part of their normal care by the PWS Centre of Reference at CHU de Toulouse.

For the control group of untreated children:

[figure not shown]
Since treatment with OT is not authorised, no child with PWS currently benefits from this treatment. For the group of control patients, the team at the reference centre will present the study by telephone to the families whose children meet the inclusion criteria ahead of a planned hospital stay at the reference centre. They will be included after the signature of the informed consent form by the parents or legal representative. Approximately 40 children with PWS are born in France every year. The inclusion period of 18 months will therefore be sufficient to include the 18 patients planned in this group.

After an adequate reflection period (between 2 and 10 days), if the parents agree to participate in this protocol they will contact one of the investigators at the reference centre who will organise the inclusion visit at CHU de Toulouse. The children will be hospitalised at CHU de Toulouse in the PWS reference centre, only one parent may sleep in the room with the child, the other may be accommodated in a suitable facility close to the Children's Hospital.

We will also explain to the family that, with some exceptions, participation in the study will not extend the duration of hospitalisation of these children for the routine assessments carried out, which is generally 3 days. The study will thus be carried out during a routine hospital stay in the reference centre.

7. STRATEGY OF THE STUDY

7.1. STRATEGY OF THE STUDY

7.2. COMPARISON STRATEGY

In the 18 babies included in the OTBB2 study we have not observed a serious adverse effect linked to OT. These children appear to have improved from the point of view of behaviour, development, communication and social skills. We wish to compare them to a control group of children with PWS not treated with OT, agematched and monitored in a comparable manner at the reference centre in order to analyse the long-term effect of OT. This strategy will allow us to document the modifying effect of early treatment with OT on the course of the disease.

8. ASSOCIATED TREATMENTS AND PROCEDURES

Chronic treatments will be continued and noted. In general, there are few at this age. Growth hormone treatment is started during the second semester of life. This treatment has also been started according to recommendations in the children included in the OTBB2 protocol. No treatment will be forbidden due to participation in the study.

9. OUTCOME MEASURES

9.1. PRIMARY OUTCOME MEASURE

The primary outcome measure is the score for the domain of Communication obtained using the Vineland II adaptive behaviour evaluation scale (cf. appendix 2).

This tool, which has been validated in France from the age of 1 year in different populations (autism, attention deficit/hyperactivity disorder, mental retardation, etc.), allows for the multidimensional assessment of skills and disabilities in daily living.

The validity of this tool has been tested in different populations with and without intellectual deficiency, aged from 3 to 16 years. Vineland II is configured to have a mean of 100 and a standard deviation of 15 (Sparow, 2015).

This tool has several applications, including the evaluation of the effects of various treatments or clinical interventions on the level of adaptive functioning.

This questionnaire is adapted to PWS and is currently used in the care of the children monitored at the reference centre. It has been the subject of a recent publication concerning the effect of growth hormone in a population of 96 children and adolescents with PWS aged from 4 to 21 years (Dykens *et al.*, 2016).

For children aged under 7 years, Vineland II examines four domains: Communication, Daily Living Skills, Socialisation and Motor Skills.

The 4 domains are summarised in a composite score for adaptive behaviour which is defined as the execution of activities of daily living required for personal and social autonomy.

Vineland II is based on standard scores for describing the global functioning of a person and his/her level of functioning in each of the domains of adaptive behaviour. A standard score indicates the deviation between the raw score of the subject and the mean gross score, taking into account the standard deviation in the distribution of gross scores.

9.2. SECONDARY OUTCOME MEASURES

The secondary outcome measures are:

- Scores in the fields Daily living skills, Socialisation and Motor skills, and the composite score for adaptive behaviour on the Vineland II scale
- o The CBCL (Child Behaviour Check List questionnaire, cf. appendix 3), often used to assess the psychopathology of patients (behavioural and emotional disorders) and in particular those with PWS (Dykens *et al.*, 2007, Skokauskas *et al.*, 2012, van Lieshout *et al.*, 1998). We will use the version aimed at children from 1.5 to 5 years of age. The CBCL is usually completed by the parents at home prior to their arrival and allows an global score to be obtained, as well as a score for the following 6 sub-scales:
 - Anxiety / Depression
 - Withdrawal
 - Emotional reactivity
 - Somatic complaints
 - Attention problems
 - Aggressive behaviour

The results are expressed as a "total problem" score and in sub-scores. For the "total problem" scale, T scores from 50 to 59 are normal; T scores from 60 to 63 are borderline; above 63 are pathological.

BSID-III (Bayley Scales of Infant and Toddler Development, 3rd edition, N. Bayley, 2006) is a standardised test designed to measure the global development of infants/young children aged from 1 to 42 months. This assessment battery examines all the spheres of development of the child. It is composed of 5 scales evaluating cognitive abilities, language (receptive and expressive) and motor skills (fine and gross) administered by the psycho-motor therapist of the reference centre. This test will be used regardless of the age of the child, taking account of the developmental delay observed in patients with PWS. The French translation, adaptation and validation of BSID-III form the subject of a national PHRC started in 2012 in Toulouse (principal investigator: [name]) and which will finish in December 2016. We have access to the final French version and are in contact with [name] who led this study and used this version. The French standards must be available during 2017. The Bayley development scales are those most frequently used in clinical research. We are working with the neonatal

department of CHU de Toulouse, and in particular with [name] who began using this test as part of the routine evaluation and care of her patients. It therefore seems relevant to use the most recent version of this scale. [name] believes that there is no problem using this test at the age of 4 years, even if the upper age limit is 42 months, given that these children have a developmental delay. In order to rate the competences of the child in detail and make qualitative observations, the application of the BSID-III scale will be filmed. The use of video media for rating this test is standard practice.

- o The assessment of eating behaviour, comprising:
 - a questionnaire on eating behaviour (cf. Appendix 4) is designed and used in clinical routine by the psychologist of the PWS Reference Centre in Toulouse. Indeed, no validated scale currently takes into account the eating behaviour problems encountered specifically in children with PWS, particularly at this age. It is completed during the interview with the parents.
 - a filmed assessment of eating behaviour during a meal.
- o The assessment of orality, comprising:
 - a recording of the voice
 - a videofluoroscopy of swallowing, which represents the "gold standard" for the objective assessment of swallowing problems. It will be carried out and interpreted by the speech and language pathologist of the Reference Centre who carries these out routinely. This is a video radioscopy, the recorded images of which can be reviewed and discussed after the examination, by another expert if need be. The contrast medium used for the radioscopy of the swallowing process is Micropaque®, produced by Laboratoire Guerbet (cf. SPC, appendix 5). It is an oral suspension. In the context of the trial, each child will receive 10 ml of Micropaque® diluted in 20 ml of apple juice.
- The cerebral activity, studied by BOLD effect in functional MRI (carried out at INSERM U825 in Baudot ward, Purpan Hospital under the responsibility of [name], the head of this unit). Two types of acquisition will be carried out: a morphological MRI and a resting-state functional MRI (rs-fMRI). No injection of contrast medium will be administered to the subjects during this examination. The examination will last approximately 20 minutes. This examination has already been carried out during the OTBB2 study on the 18 infants with PWS.
- Oculometric tests, which allow the gaze position and eye movements in response to visual or auditory stimulation to be studied. The type of eye movement, saccadic eye movements and the position on which the observer focuses are good indicators of the type of social interaction. These oculometric tests are carried out using a TOBII eye tracker, which uses pupillary and corneal refraction of infrared light to track the rotation of the eyes. Eye-tracking is innovative technology, powerful and non-invasive, which is widely used to study social cognition and the perception of emotions, particularly in young children with autism. We have acquired this device which will be used in a study on young children with PWS under the initial supervision of the PhD student ([name]) whose thesis is co-directed by [name] of the Brain and Cognition Research Centre (CerCo) and [name].

- Circulating rates of acylated and non-acylated ghrelin and certain peptides and neuropeptides involved in regulation of the appetite (leptin, cortisol, insulin, GLP-1, PYY, pancreatic polypeptide, orexin A, αMSH).
- The evolution of height and weight and clinical parameters collected on a routine basis.

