6. ELIGIBILITY CRITERIA

6.1. INCLUSION CRITERIA

The OTBB2 study finished in July 2014 and it was possible to include 18 babies who were seen regularly at the reference centre; all the children included in OTBB2 will be offered the study. This will be the treated group.

For the treated group:

- Male or female child with PWS (genetically confirmed diagnosis) who has participated in the OTBB2 study (i.e. has received intranasal administrations of OT for 7 days before the age of 6 months), aged from 3 to 4 years at the time of inclusion.

For the untreated control group:

- Male or female child with PWS (genetically confirmed diagnosis) aged from 3 to 4 years at the time of inclusion and never treated with OT, age-matched to the children treated with OT plus or minus 3 months.

The parents (or legal representative) must have signed the consent form and the child must be registered with a social security regime.

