12.2. STATISTICAL METHODS USED

A statistical analysis plan (SAP) will be defined before the database is frozen. All the statistical analyses detailed in the SAP will be carried out by a statistician from the Methodological Support Unit for Research of CHU de Toulouse using Stata® or SAS® software.

All the study variables will be presented by exposure group (children having received early OT versus children never treated with OT) using the descriptive statistics appropriate to each type of variable.

 Continuous variables: number of non-missing observations, median, 1st and 3rd quartile, minimum and maximum, average and standard deviation.

¹ Armitage, P., G. Berry, and J. N. S. Matthews. 2002. Statistical Methods in Medical Research. 4th ed. Oxford: Blackwell. Chow, S.-C., J. Shao, and H. Wang. 2008. Sample Size Calculations in Clinical Research. 2nd ed. New York: Dekker. Dixon, W. J., and F. J. Massey, Jr. 1983. Introduction to Statistical Analysis. 4th ed. New York: McGraw–Hill.

² Julious, S. A. 2004. Tutorial in biostatistics: Sample sizes for clinical trials with Normal data. Statistics in Medicine; 23:1921-1986.

 Categorical variables: number of non-missing observations, number and percentage of each modality (percentages will be calculated on the basis of the non-missing observations).

Taking into account the limited staff complement, the analyses will primarily be exploratory. For the primary and secondary outcome measures, the total scores and scores per dimension on the different scales (Vineland-II, CBCL, BSIDIII) will be calculated according to the recommendations of the authors. Missing data may be imputed according to the recommendations. The differences in scores obtained in the group of children exposed to treatment before the age of 6 months and the group of control children who have never been treated with oxytocin will be calculated, as well as their confidence intervals at 95%. Comparisons between the exposure groups will be made using a Student's test or a Mann-Whitney test for the scores for the different scales and continuous variables and with a Fisher's exact test for categorical variables. No correction will be applied for the multiplicity of the tests.

For the MRI, the analyses will be made by the MRI team using the same method as that used in the OTBB2 study (article under publication).

All the statistical comparisons on the principal and secondary criteria will be carried out with an alpha risk of 5%.

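### BSID-III is to be used past its stated 42-month limit, with no score named and no age adjustment for the half of the 3 to 4 year window above that limit

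*Protocol*

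**What the plan says.** Section 9.2 introduces BSID-III as a standardised test "designed to measure the global development of infants/young children aged from 1 to 42 months", and then sets that range aside for this study: "This test will be used regardless of the age of the child, taking account of the developmental delay observed in patients with PWS". It acknowledges the limit and reports a colleague's opinion that "there is no problem using this test at the age of 4 years, even if the upper age limit is 42 months", because these children are delayed. It also mentions French standards expected during 2017.

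Section 6.1 requires children to be "aged from 3 to 4 years at the time of inclusion", with controls matched on age to within 3 months.

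Section 12.2 says that totals and dimension scores of Vineland-II, CBCL and BSID-III "will be calculated according to the recommendations of the authors". Scale scores are then compared between groups by a Student or Mann-Whitney test. No term for age is mentioned.

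**The concern.** Two questions are run together. One is whether the items can sensibly be given to a delayed 4-year-old. Delay makes a ceiling effect less likely, so it supports doing so. The other is what the resulting score means. A norm-based score compares a child with reference children of the same age, and delay in the tested child does not create reference values above 42 months. For older children, the instruction to test at any age and the instruction to score as the authors recommend do not fit together on the protocol's own description of the test.

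The protocol does not say whether the BSID-III score to be analysed is raw, scaled, composite or age-equivalent. Each reading has a cost. Norm-based scores would be missing above 42 months, or too lenient if the oldest norms were applied. Raw scores exist for every child but rise with age, and the planned tests ignore age. At stake is the global development comparison. Among the three scales named in Section 12.2, only BSID-III has a stated range that ends inside the inclusion window: the CBCL version covers 1.5 to 5 years, and Vineland-II was tested from 3 to 16 years.

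**Working it through.** **The plan's own figure.** The only computed design figure is 17 per group for the Vineland-II Communication score (difference 15, SD 15, two-sided 5%, power 80%). The t-based solution is 16.71, rounded up to 17, so it reproduces. It does not concern BSID-III, for which no power is stated.

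**Share of the age window above the limit.**
- If 3 to 4 years means 36 to 48 months: (48 − 42)/(48 − 36) = 6/12 = 50%.
- If it runs to the fifth birthday: (60 − 42)/(60 − 36) = 18/24 = 75%.

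**Treated children above the limit.** Inputs: OTBB2 inclusions from May 2013 to July 2014 in infants under 6 months (Section 3.1); inclusions here from January 2017 for 18 months (Section 10.1). Assumptions: entry date *e* uniform from month 4 to month 19, counted from January 2013; entry age *a* uniform over 0–6 months (mean 3) or 3–6 months (mean 4.5). Age at date *d* is d − e + a. The share older than 42 months is therefore (d − 42 − 4 + mean a)/15.

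- 1 January 2017 (d = 48): (2 + 3)/15 = 33%, or 6.0 of 18; (2 + 4.5)/15 = 43%, or 7.8 of 18. Children already past 48 months need e < a. The mean of (a − 4) above zero is 2/6 or 2/3; divided by 15 this gives 2.2% or 4.4%, that is 0.4 or 0.8 children. Between 42 and 48 months: 5.6 to 7.0.
- 22 March 2017 (d = 50.7, the date of the protocol version, used only as a second reference point): (4.7 + 3)/15 = 51%, or 9.2; (4.7 + 4.5)/15 = 61%, or 11.0. Past 48 months: (4.7²/12)/15 = 12.3%, or 2.2; (4.5 − 1.3)/15 = 21.3%, or 3.8. Between 42 and 48 months: 7.0 to 7.2.

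So about 6 to 7 of 18 are inside the window but above the limit at either date. The share at the actual visit depends on scheduling. Simulating eligible windows (entry age 0–6 months, 48-month upper limit, January 2017 start) gives about 32% above 42 months if each child is seen at the earliest eligible date, and about 74% if visits are spread evenly over each child's eligible window.

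**Consequence under each reading of the score.**
- *Norm-based, older children unscored.* If half of each group were lost, 9 per group would remain. Power of a t-test for a 1 SD difference would be about 51%, against 83% with 18 per group (illustration only).
- *Norm-based, 42-month norms applied to older children.* A child of 48 months is judged as if 6 months younger: 6/42 = 14% on a ratio-type quotient. That is the extreme age and a score type that the protocol does not plan. The error runs the same way in both groups.
- *Raw score, unadjusted.* Expected group difference = treatment difference + (raw-score gain per month) × (difference in mean age). Matching bounds the age difference at 3 months (3/42 = 7%), which requires every pair to differ fully in the same direction. If pair differences are uniform within ±3 months, their SD is 6/√12 = 1.73. The mean over 18 pairs then has SD 1.73/√18 = 0.41, and a 95% limit of 1.96 × 0.41 = 0.8 months (0.8/42 = 2%).

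**The case against.** The strongest reply has four parts.

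- *The off-range use is disclosed and argued.* This stands: it is not an oversight. But the argument given covers giving the test, not scoring it.
- *No norm-based BSID-III score is actually planned.* This also stands. A reader might infer from the description as a standardised test, the reference to French standards and the authors' scoring rule that the plan rests on scores that do not exist above 42 months. The documents do not support that: they name no BSID-III score type, and neither the manual's rules for older delayed children nor the age range of the French standards is shown. What can be said is that norm-based scores have no stated basis above 42 months.
- *The choice of score belongs in the statistical analysis plan.* This is true of the choice alone. The protocol, however, already fixes use at any age, scoring by the authors' rules and a two-group test without age. A plan faithful to those statements inherits the conflict whichever score it picks.
- *Matching removes the problem.* It removes much of it, since any leniency acts in the same direction in both groups and the mean age gap is likely to be well under a month. It does not remove all of it, and two children in a pair can fall on opposite sides of 42 months.

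**Conclusion.** The point holds in a limited form. BSID-III is planned outside its stated range for half of a 36 to 48 month window, affecting about 6 to 7 of the 18 treated children at early 2017 dates under uniform-entry assumptions. For those children the scoring rule has no stated basis. If raw scores are used instead, the planned tests leave age unadjusted.

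Three stronger readings are tempting and should be resisted:
- That 9 to 11 treated children fall in the affected band by March 2017: this count includes 2.2 to 3.8 who would already be past 48 months.
- That any age gap turns into an apparent treatment effect of 7%: this is the extreme bound. About 2% is the 95% limit if pair differences are uniform.
- That BSID-III is the only directly tested and filmed outcome: Sections 9.2 and 10.5 also provide for a filmed meal, recorded videofluoroscopy and eye-tracking.

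BSID-III is one secondary measure in a study whose analyses are described as mainly exploratory. The Vineland-II primary conclusion is untouched. The change is worth making because it is cheap, not because the study depends on it.

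**What to change.** State in Sections 9.2 and 12.2 that:

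- BSID-III is compared between groups, in all children, on the raw score of each scale, using a linear model with group and chronological age at testing, and reporting the adjusted difference with its 95% confidence interval;
- age equivalents are a supportive analysis only, since they depend on the same reference range;
- norm-based scores are reported descriptively, and only for children aged 42 months or less at testing, with the number contributing in each group.

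The cost is wording and one model per scale. The test sheets already supply raw scores, so no visit, test or child is added. The drawback is that the between-group result will not be on the familiar mean-100 scale, which makes it harder to set beside published BSID-III figures.

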3.3. RISK/BENEFIT BALANCE

The risks linked to participation in this study are:

- The risk linked to X-rays is low because with current methods the irradiation is 20 μGray which is far lower than 1 non-digital chest X-ray.
- There is currently no known risk linked to MRI examination other than the standard contraindications. Patients with PWS routinely have cerebral imaging carried out generally after 2 years. There is no need for anaesthesia or sedation. MRI examinations have already been performed by our team on patients with PWS with no major difficulty in the vast majority of cases.

It is important to note that all these examinations are likely to be carried out as part of the care of the children with PWS at the Reference Centre.

- For the oculometric assessment, no undesirable effect is expected with the eye-tracking system, a non-ionising and non-invasive technique. The infra-red light emitted by the eye tracker (TOBI) is not harmful to the human eye.

Taking account of the minimal risks incurred by the subjects, the risk/benefit balance for the children with PWS can be considered acceptable for this study. The benefit is above all collective: if an improvement is observed in the long-term state of health of the children with PWS treated with OT during their first 6 months of life, this will document our hypothesis of a positive long-term effect and will support our request for market authorisation in the near future, so that all babies with PWS can be treated.

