4.3. Contre-indications

Ce médicament est contre-indiqué en cas de :

- Hypersensibilité à la substance active ou à l'un des excipients
- Perforation ou occlusion intestinale avérée ou suspectée, y compris sténose du pylore
- Plaies récentes ou érosions de l'oesophage ou du tube digestif ou hémorragie gastro-intestinale
- Entérocolite nécrosante
- · Mégacôlon ou mégacôlon toxique
- Lâchage de suture postopératoire. Le sulfate de baryum ne doit pas être administré immédiatement avant, et jusqu'à sept jours après une intervention chirurgicale gastro-intestinale, y compris en cas de résection endoscopique, de polypectomie à l'anse, ou de biopsie à chaud du côlon. Le médicament ne doit pas être utilisé si des fuites postopératoires sont prévisibles. Ne pas utiliser le produit en cours de radiothérapie du cou, du thorax (si utilisation orale) ou de l'abdomen et jusqu'à quatre semaines après la radiothérapie.

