Des fuites de baryum dans le rétropéritoine ou dans le médiastin peuvent se manifester par quelques symptômes immédiats mais

Des juites de baryont dans le réctivolre du dans le médiosain peuvent se mainester par queueurs symptomes immediats mais un choc endotoxique retardé, qui se révèle fréquemment fatal, peut survenir 12 heures plus tard. En cas de perforation intestinale, le passage du sulfate de baryum dans la cavité abdominale peut être à l'origine d'abcès, d'inflammations, de péritonites, de granulomes et d'adhérences dont l'évolution peut être fatale et qui nécessitent un recours à la chirurgie.

Inhalation

Si le produit est utilisé oralement, il convient de surveiller particulièrement les patients souffrant de troubles respiratoires et de troubles de la déglutition tels que la dysphagie, ainsi que de troubles de la vigilance, car il existe un risque d'inhalation. Les vomissements après l'administration orale de sulfate de baryum peuvent provoquer une pneumonie d'inhalation.

Le baryum ne doit pas être administré à des patients ayant des antécédents de fausse route alimentaire. Si l'utilisation du baryum est absolument nécessaire chez ces patients, une prudence particulière s'impose. Dans le cas de passage dans le larynx, l'administration du produit doit être immédiatement interrompue.

Population pédiatrique

Chez les patients hautement prédisposés à l'inhalation (nouveaux-nés) la procédure doit débuter par une faible dose orale. L'inhalation dans l'arbre trachéobronchique peut survenir lors de l'administration de suspension buvable de sulfate de baryum en bouteille à des nourrissons et lors de l'administration de quantités importantes par cathéter. Chez les nourrissons, l'inhalation peut entraîner un arrêt cardio-respiratoire avec issue fatale. L'inhalation de petites quantités peut occasionner une inflammation des voies respiratoires et une pneumopathie.

Sujets âgés

Chez les patients hautement prédisposés à l'inhalation (sujets âgés et ayant subi un AVC), la procédure doit débuter par une faible

Résumé des caractéristiques du produit - MICROPAQUE, suspension buvable ou rec... Page 3 sur 5

Surcharge liquidienne

Une surcharge liquidienne due à l'absorption de l'eau contenue dans les suspensions de sulfate de baryum a été rapportée. Les enfants et les patients insuffisants rénaux ainsi que les enfants atteints de la maladie de Hirschsprung sont plus exposés à une intoxication par l'eau.

Population pédiatrique

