4.7. Effets sur l'aptitude à conduire des véhicules et à utiliser des machines

Les effets sur l'aptitude à conduire des véhicules et à utiliser des machines n'ont pas été étudiés. Cependant, les propriétés pharmacodynamiques et pharmacocinétiques du sulfate de baryum ne sont pas de nature à avoir un effet sur l'aptitude à ce des véhicules et à utiliser des machines.

Les effets indésirables liés à l'utilisation de Micropaque sont présentés dans le tableau ci-dessous par Système Organe Classe et $\frac{par fréquence en utilisant les catégories suivantes : très fréquent (<math>\geq$ 1/10), fréquent (\geq 1/100 à 1<1/10), peu fréquent (\geq 1/1000 à 1<1/1000), rare (\geq 1/10000 à <1/10000), très rare (<1/10000), fréquence indéterminée (ne peut être estimée sur la base des données des données (\geq 1/10000).

Système Organe Classe	Fréquence : effet indésirable

Résumé des caractéristiques du produit - MICROPAQUE, suspension buvable ou rec... Page 4 sur 5

Affections hématologiques et du système lymphatique	Fréquence indéterminée :
	En cas d'intravasation : coagulation intravasculaire disséminée
Affections du système immunitaire	Fréquence indéterminée : réaction anaphylactique, réaction anaphylactoïde, hypersensibilité
Affections gastro-intestinales	Fréquence indéterminée : occlusion intestinale, vomissement, diarrhée, douleurs abdominales, fécalome, distension abdominale constipation, nausée, flatulence ; en cas de perforation intestinale péritonite
Affections respiratoires, thoraciques et médiastinales	Fréquence indéterminée : pneumopathie d'inhalation, fibrose pulmonaire
Affections du système nerveux	Fréquence indéterminée : présyncope
Affections de la peau et du tissu sous-cutané	Fréquence indéterminée : urticaire, rash généralisé

Le parahydroxybenzoate de méthyle sodé et le parahydroxybenzoate de propyle sodé peuvent provoquer des réactions d'hypersensibilité immédiates et retardées.

Les produits de contraste contenant du sulfate de baryum peuvent provoquer des réactions d'hypersensibilité d'intensité variable. Très rares, ces réactions peuvent toutefois apparaître des la première administration. L'administration du produit doit alors être interrompue immédiatement et un traitement spécifique doit être mis en place.

Dans de très rares cas, l'administration de sulfate de baryum peut provoquer la formation de fécalomes barytés.

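### Section 9.2 gives barium contrast to every child with no withholding or stop rule, although the annexed SPC restricts barium after food aspiration, and the risk sections cover only radiation

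*Protocol*

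**What the plan says.** Section 9.2 lists videofluoroscopy of swallowing as part of the secondary assessment of orality. It names Micropaque as the contrast medium, refers to the SPC in appendix 5, and fixes the dose: "each child will receive 10 ml of Micropaque® diluted in 20 ml of apple juice". Section 10.5 schedules the examination within the three-day stay, again without a condition.

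The annexed SPC, section 4.4 (Inhalation), says: "Le baryum ne doit pas être administré à des patients ayant des antécédents de fausse route alimentaire". It then gives the exception: "Si l'utilisation du baryum est absolument nécessaire chez ces patients, une prudence particulière s'impose". If the product passes into the larynx, "l'administration du produit doit être immédiatement interrompue". SPC 4.3 lists separate contraindications, the first being "Hypersensibilité à la substance active ou à l'un des excipients". The SPC table of adverse reactions includes "pneumopathie d'inhalation, fibrose pulmonaire" and anaphylactic reactions.

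Section 6.2 has one note allowing an examination to be left out: "If a patient presents a contraindication for MRI, he/she can be included in the study but the MRI will not be carried out". On the risk of the swallowing examination, 3.3 begins "The risk linked to X-rays is low because with current methods the irradiation is" and goes no further than the radiation dose. Section 11.2 likewise expects no reaction because the radiation is low. It then treats any serious reaction that it does not list as unexpected.

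**The concern.** The main text tells the investigator to give barium to every child, while the annex that the text cites tells the clinician not to give it to some. Nothing in the protocol's own text says which instruction prevails. Section 16 commits investigators to all points of the protocol except in urgent therapeutic situations, so on a literal reading a clinician who withholds barium as the SPC directs departs from 9.2.

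The population makes this more than a formality. Section 3.1.1 describes sucking and swallowing difficulties in all newborns with the syndrome. The article in the first appendix names aspiration as a possible life-threatening complication in early infancy. At stake are the safety of a young child in one research examination and the completeness of the risk statement. There is also a reporting effect: a reaction already known for barium would go to the agency and the ethics committee as unexpected.

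**Working it through.** The only arithmetic is the volume per child: 10 ml + 20 ml = 30 ml of mixture. The rest is a comparison of text.

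1. **Who receives barium.** Sections 9.2 and 10.5: every child. Neither 6.1 nor 6.2 asks about aspiration history or a Micropaque contraindication.

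2. **Who should not.** SPC 4.4: patients with a history of food aspiration, unless use is absolutely necessary. This is a precaution with an exception, not a contraindication under 4.3. SPC 4.3 separately lists 6 contraindication items: hypersensitivity; perforation or obstruction (including pyloric stenosis); recent wounds, erosions or bleeding of the digestive tract; necrotising enterocolitis; megacolon; post-operative suture leakage.

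3. **Does the exception apply?** Videofluoroscopy serves a secondary outcome, and 12.2 describes the analyses as mainly exploratory. The study by itself therefore does not make barium absolutely necessary. A clinical indication in a given child might.

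4. **Is there a rule in the main text that resolves it?** Section 6.2 has 1 skip note for MRI and 0 for barium, and takes up none of the 6 items in SPC 4.3. Section 10.6 covers withdrawal from the study, not stopping an examination. The SPC's stop instruction on laryngeal passage appears nowhere in the main text.

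5. **Are the risks named?** The SPC reaction table covers 6 organ classes (blood, immune, gastrointestinal, respiratory, nervous system, skin). Sections 3.3 and 11.2 name 0 of them as a contrast-medium risk. They do discuss MRI and eye-tracking, and 11.2 also covers blood sampling; for the swallowing examination they discuss radiation only.

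6. **What follows for reporting.** Section 11.1 makes the protocol, and 11.2 in particular, the reference for expectedness. Serious aspiration pneumonia or anaphylaxis from barium is not listed in 11.2, so it is unexpected by definition. Under 11.4 it is declared as such to the agency and the ethics committee. The error is over-reporting; no event is hidden.

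**The case against.** The strongest reply is that 9.2 points to the SPC and the SPC is annexed, so the restriction, the exception and the stop instruction are already in the team's hands. The dose sentence can be read as fixing volume and dilution only. Sections 3.3, 10.7 and 11.2 also present these examinations as part of usual care at the reference centre, so some children may have the videofluoroscopy anyway. A speech and language pathologist who performs it routinely carries it out, during an inpatient stay, and 11.3 keeps a child in hospital after any adverse event until parameters return to normal. The evidence on aspiration in the appended article concerns infancy, not ages 3 to 4. The effect on 11.2 is in the cautious direction. Section 15.1 already requires an explanation for missing data, and 12.2 already gives non-missing counts by group.

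All of this is accurate and lowers the practical risk. It does not close the gap. A reference next to an instruction covering each child is not a withholding rule, and the MRI note shows how this protocol writes one. Section 10.7 also counts videofluoroscopy among the additional assessments that make up the burden of the study, so routine-care status does not cover every child. No safeguard cited supplies the stop rule or corrects 11.2.

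**Conclusion.** The concern holds. As written, 9.2 would give barium to a child with a history of food aspiration, whom the protocol's own annex says should not normally receive it, for a secondary measure. Sections 3.3 and 11.2 leave out the risks of the contrast medium.

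The size is limited and cannot be put as a number. It concerns only children with an aspiration history or an SPC 4.3 contraindication among the 36 planned; the documents do not give their number, and none is assumed here. The conclusion rests on reading 9.2 literally and on the main text containing no other rule. Nothing is claimed about the information sheet, which was not available. The primary outcome, the sample size and error control are untouched. This should be fixed because it bears on a child's safety and is cheap to correct.

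**What to change.** - In 6.2 or 9.2, add a note parallel to the MRI note. A child with a history of food aspiration or a Micropaque contraindication can be included, but the barium videofluoroscopy is not carried out unless it is clinically necessary, and then with the caution the SPC requires.
- In 9.2 or 10.5, state that administration stops at once if the product passes into the larynx.
- In 3.3 and 11.2, add the contrast-medium risks listed in the SPC, at least aspiration pneumonia and hypersensitivity or anaphylactic reactions.
- Report by group how many children were not examined for this reason. The counts in 12.2 show how many values are missing but not why. These absences are likely to be related to swallowing function, so the reason matters when the groups are compared.

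The cost is a short protocol amendment and a matching line in the information sheet if it is not already there. A few videofluoroscopies may be missing from one exploratory secondary measure.
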